4.6. Pharmacodynamic Analyses

The PD effects of ALXN1210 administered SC/IV will be evaluated as follows:

- Changes and percent changes in serum total and free C5 concentration over time.
- Change and percent change in cRBC hemolysis over time.

Pharmacodynamic data will be listed for each individual subject and absolute (observed values) as well as changes and percent changes from Baseline will be summarized at each time point by treatment group.

Individual and mean percent change from baseline versus nominal time profiles will be presented graphically for each PD parameter.

4.7. Pharmacokinetic/ Pharmacodynamic Analysis

An exploratory analysis may be performed to examine exposure-response relationships between ALXN1210 serum concentrations and the PD endpoints total C5, free C5, and/or cRBC hemolysis. If completed, the analysis will be the responsibility of Alexion and results will be described in the CSR and will be the responsibility of Alexion.

4.8. Immunogenicity Analyses

Immunogenicity, as measured by ADA, will be summarized in tabular form (number and percentage of subjects developing ADA) by treatment group. Titer result will be presented in frequency tables, descriptive statistics and by-subject listings.

4.9 Methods for Withdrawals, Missing Data, and Outliers

The individual serum concentration data and the actual timing of study drug administration and blood sampling will be used throughout the analyses. If there is any doubt about the actual time at which a sample was taken, then the scheduled time will be used. For PK data analysis, please see Section 4.5 regarding the handling of missing and BLQ values. For PD data analysis, there will be no imputation for missing values.

If medication dates are incomplete and it is not clear whether the medication was concomitant, it will be assumed to be concomitant.

AEs with unknown start date/time will be assumed to be treatment-emergent unless the end date/time is known to be before the first administration of study drug. Otherwise missing or partial dates will be listed as such.

There will be no further imputation of missing data (i.e., subjects who prematurely discontinue from the study will not be included in summary statistics or analyses beyond the time of discontinuation).

Depending on the extent of missing values, the appropriateness of the methods described for handling missing data may be reassessed prior to database lock (to examine the sensitivity of results to handling of missing data).

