8.1. Overall Study Design

This is a Phase 1 study designed to evaluate the safety, tolerability, PK, PD, and immunogenicity of a single 400 mg dose of ALXN1210 SC compared to a single 400-mg dose of ALXN1210 IV or placebo SC in 42 healthy subjects. All subjects will be screened for eligibility in the study after providing signed and dated institutional ethics committee-approved written informed consent to participate and before any study specific screening procedures are performed.

Subjects who fail to meet eligibility criteria may not be rescreened for participation in the study, unless the condition that led to eligibility failure is transient, self-limited, and easily treatable, and is expected to be resolved at the time of dosing, as agreed by the investigator and medical monitor.

Six subjects will initially be randomly assigned in a 2:1 ratio to Cohort 1a, in a blinded fashion, to receive either a single 400-mg dose of ALXN1210 SC or single dose of placebo SC (Figure 1). The Safety Review Committee (SRC) will evaluate the first 48 hours of post-dose clinical safety data for subjects in Cohort 1a before enrollment into Cohorts 1b or 2 may begin. Thirty-six subjects will then be randomly assigned, in a 2:1 ratio, to either Cohort 1b (N=24) or Cohort 2 (N=12). Within Cohort 1b, the 24 subjects will further be randomly assigned, in a 5:1 ratio and blinded fashion, to receive either a single 400-mg dose of ALXN1210 SC or a single dose of placebo SC, respectively. The 12 subjects in Cohort 2 will receive a single 400 mg dose of ALXN1210 IV in an open-label fashion.

Figure 1: Study Diagram

Abbreviations: A = active drug; IV = intravenous; P = placebo; SC = subcutaneous; SRC = Safety Review Committee Note: The SRC will review the first 48 hours of post-dose safety data from Cohort 1a before enrollment into Cohorts 1b or 2 may begin.

At the sponsor's discretion, up to 8 additional subjects (2 subjects each in Cohorts 1a and 1b and 4 subjects in Cohort 2) may be enrolled into the study if 2 or more subjects discontinue within 3 months for reasons other than drug-related AEs, and after consultation with the SRC. All enrolled subjects will be included in analyses as appropriate. Subjects in Cohorts 1a and 1b will be combined for analyses. Subjects who withdraw from the study subsequent to dosing will be followed for safety assessments through the last scheduled study visit, if possible.

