16. ADVERSE EVENT MANAGEMENT

The investigator is responsible for detecting, assessing, documenting, and reporting all AEs. All AEs will be recorded from the signing of ICF until study completion. There is no time limit for SAEs that are considered causally related.

All observed or volunteered AEs, regardless of causal relationship, must be reported and recorded in the data capture system. Adverse events reported by the subject and/or parent or legal guardian, and/or identified in response to an open-ended question from study personnel, or revealed by observation, physical examination, or other study procedures must be collected and recorded.

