16.8. Exposure During Pregnancy and Lactation

Pregnancy data will be collected during this study for all subjects.

For all Alexion products, both in development or postapproval, exposure during pregnancy must be recorded and followed. Exposure during pregnancy, also called exposure in utero, can be the result of either maternal exposure or transmission of drug product via semen following paternal exposure.

If a female subject participating in this study or a male subject's female partner becomes or is found to be pregnant while being treated or exposed to study drug, the investigator must submit the "Pregnancy Reporting and Outcome/Breast Feeding Form" to Alexion or designee via the same methods as SAE reporting. Female subjects who become pregnant will be discontinued from dosing, but will continue to be followed for safety where feasible. Male subjects may

continue in the study if an accidental pregnancy of their female partner occurs despite adequate contraception.

The female subject should be followed until the outcome of the pregnancy is known (spontaneous miscarriage, elective termination, normal birth or congenital abnormality), even if the subject discontinues study drug or discontinues from the study. When the outcome of the pregnancy becomes known, the form should be updated and returned to Alexion or designee. If additional follow-up is required, the investigator will be requested to provide the information.

Pregnancy in itself is not regarded as an AE, unless there is a suspicion that investigational product may have interfered with the effectiveness of a contraceptive medication. However, complications of pregnancy and abnormal outcomes of pregnancy are AEs, and many may meet criteria for an SAE. Complications of pregnancy and abnormal outcomes of pregnancy, such as ectopic pregnancy, spontaneous abortion, intrauterine fetal demise, neonatal death, or congenital anomaly, would meet the criteria of an SAE and therefore should be reported as an SAE. Elective abortions without complications should not be handled as an AE.

Exposure of an infant to an Alexion product during breastfeeding should also be reported on the "Pregnancy Reporting and Outcome/Breast Feeding Form." Any AEs an infant experiences following breastfeeding are to be reported to Alexion or designee.

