18.6. Safety Analysis

Safety analyses will be performed on the safety population, and will be reported by each cohort. Safety analyses will include an analysis of all AEs, ECGs, clinical laboratory data, physical examinations, and vital sign measurements, and will be presented using descriptive statistics. No inferential statistical analyses are planned on the safety parameters of this study. The incidence of treatment-emergent AEs and SAEs will be summarized, by system organ class and preferred term for each cohort and overall, by relationship to study drug. Treatment-emergent AEs will also be summarized by cohort and overall by severity. Serious AEs and AEs resulting in withdrawal from the study will be listed. Subjects having multiple AEs within a category (eg, overall, system organ class, preferred term) will be counted once in that category. For severity tables, a subject's most severe event within a category will be counted.

Changes from baseline in vital sign measurements and laboratory assessments (eg, chemistry, CBC with differential, and urinalysis) will be summarized by each cohort. Laboratory parameter values will be graded according to the CTCAE. Shift tables by cohort will be produced for these laboratory parameters. These tables will summarize the number of subjects with each baseline grade relative to the reference ranges and changes to the worst highest grade assessed post-dose during the study.

The ECG parameters will be measured at the specified time points, including heart rate, PR, RR, QRS, QT, and corrected QTcF intervals. The average of the triplicate ECG readings at the time points collected will be calculated, and changes from pretreatment baseline values will be assessed by each cohort.

An outlier analysis will be performed that will summarize the frequency and percentage of subjects who meet any of the following outlier criteria at each visit by cohort:

- QT, QTcF interval > 450 msec
- QT, QTcF interval > 480 msec
- QT, QTcF interval > 500 msec
- QT, QTcF interval increases from baseline > 30 msec
- QT, QTcF interval increases from baseline > 60 msec

All concomitant medications will be coded using the WHO Drug Dictionary, and the frequency and percentage of concomitant medications will be summarized.

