4.4. Safety Analysis

Safety analyses will be performed on the safety population, and will be reported by each treatment group and overall. Safety analyses will include an analysis of all

Statistical Analysis Plan

AEs, ECGs, clinical laboratory data, vital sign measurements, and physical examination results and will be presented using descriptive statistics. No inferential statistical analyses are planned on the safety parameters of this study.

Adverse Events

The incidence of treatment-emergent (after dosing) AEs (TEAEs) will be summarized using the safety population. The Medical Dictionary for Regulatory Activities (MedDRA) dictionary Version 19.0 (or higher) will be used to classify all AEs reported during the study by System Organ Class (SOC) and Preferred Term. A summary of TEAEs including the incidence of subjects who experienced TEAEs (number and percentage of subjects) and incidence of TEAEs (number of events) will be presented for each treatment group and overall, by severity and by relationship to study drug. TEAEs and serious TEAEs will be summarized by SOC and Preferred Term for each treatment group and overall, by severity, and by relationship to study drug. Treatment group will be categorized by the treatment that was actually received at the date of AE onset (i.e., ALXN1210 SC, ALXN1210 IV or ALXN1210 placebo SC). Subjects having multiple AEs within a category (e.g., overall, SOC and Preferred Term) will be counted once in that category. For severity tables, a subject's most severe event within a category will be counted. For relationship tables, a subject's event with greatest relationship to study drug within a category will be counted. In each table, SOC and Preferred Term will be presented in descending order of overall incidence rate (alphabetical order will be used in case of equal rates). All TEAEs, serious TEAEs, TEAEs resulting in withdrawal from the study, TEAEs occuring during study drug administration and AEs that occurred before first dose administration will be presented in by-subject listings.

Medical History

Medical history data will be coded using MedDRA dictionary Version 19.0 (or higher) and listed individually.

Vaccination Status

A listing of MCV4 and Serogroup B vaccination status and dates will be presented individually.

Study Drug Administration

Study drug administration data will be listed individually.

Vital Signs

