Vital signs data (systolic and diastolic blood pressure, heart rate, temperature, and respiration rate) will be listed for individual subjects. In addition, height and body weight will be listed for individual subjects. Summary statistics of absolute (observed) values and changes from Baseline will be calculated for each parameter by each treatment group.

Laboratory Data

Clinical laboratory parameters (blood chemistry, hematology, coagulation, urine chemistry, urinalysis and other laboratory results) will be listed and abnormal parameters will be flagged as high (H) or low (L) according to reference ranges. Absolute (observed) values and changes from Baseline (continuous variables) will

Statistical Analysis Plan

be summarized by each treatment group based on scheduled values. The first scheduled lab value will be used for summary analysis if repeated measurements are made at any time point.

For summary statistics, a lab value with "<" will be replaced with a numeric value by removing the "<" sign. In the listings, the values will be displayed as originally reported by the laboratory.

Laboratory parameter values will be graded according to the Common Terminology Criteria for Adverse Events (CTCAE). Parameters that are not present in this document will be omitted. Shift tables by treatment group will be produced for these laboratory parameters by grade. These tables will summarize the number of subjects with each baseline grade relative to the normal ranges and changes to the worst highest grade assessed post-dose during the study.

Electrocardiograms

Electrocardiogram parameters will be measured at the specified time points and will include heart rate, PR, RR, QRS, QT, and corrected QT interval corrected using Fridericia's formula (QTcF)(QTcF=QT/RR^1/3) intervals and will be listed individually. The average of the ECG readings at the time points collected will be calculated, and absolute (observed) values and changes from Baseline values will be summarized by each treatment group.

An outlier analysis will be performed that will summarize the frequency and percentage of subjects who meet any of the following outlier criteria at each visit by treatment group:

- QT, QTcF interval > 450 msec
- QT, QTcF interval > 480 msec
- QT, QTcF interval > 500 msec
- QT, QTcF interval increases from baseline > 30 msec
- QT, QTcF interval increases from baseline > 60 msec

Prior and Concomitant Medications

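### SAP 4.9: the explanation of the no-imputation rule, read literally, drops safety data observed after a subject discontinues from the study, contrary to SAP 4.1 and 4.4 and Protocol 18.6

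*SAP*

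**What the plan says.** SAP Section 4.9 gives rules for uncertain sampling times and for incomplete medication and AE dates. It refers to Section 4.5 for missing and unquantifiable concentrations, and says PD values are not imputed. It then states "There will be no further imputation of missing data" and explains this in a parenthesis opening with 'i.e.': "subjects who prematurely discontinue from the study will not be included in summary statistics or analyses beyond the time of discontinuation". The parenthesis speaks of summaries and analyses in general and makes no exception for safety. A last sentence allows missing-data methods to be reconsidered before database lock, depending on how much is missing.

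The safety rules are elsewhere:

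- SAP Section 4.1 makes membership of the safety population depend on dosing, not on staying in the study.
- SAP Section 4.4: "The incidence of treatment-emergent (after dosing) AEs (TEAEs) will be summarized using the safety population".
- Protocol Section 18.6: "Safety analyses will include an analysis of all AEs, ECGs, clinical laboratory data, physical examinations, and vital sign measurements".
- Protocol Section 8.1, repeated in the synopsis: "Subjects who withdraw from the study subsequent to dosing will be followed for safety assessments through the last scheduled study visit, if possible".
- ADA incidence is a safety endpoint (Protocol Section 7.1, SAP Section 2.2) but is tabulated under SAP Section 4.8.
- SAP Section 4.4 puts all treatment-emergent AEs in by-subject listings, and SAP Section 5 has the listings cover every enrolled subject.

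**The concern.** Not imputing a value and not including a subject amount to the same thing only if nothing is observed after the subject discontinues. In this study something may be, because safety follow-up is meant to continue after withdrawal. A programmer who looks for the withdrawal rule will go to SAP Section 4.9, whose title names withdrawals. There the instruction is to exclude. A programmer who starts from Section 4.4 will include. No text says which section governs.

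Safety and tolerability of SC compared with IV is a primary objective and is assessed descriptively, without inference, so the tables carry the comparison. Groups are small, and one subject is visible in a percentage. The half-life after a single 400-mg IV dose was 30.8 days (Protocol Section 5.1.1), so findings some weeks after an early withdrawal can still bear on the drug.

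**Working it through.** **The plan's own figures.** The documents give no withdrawal rate and no target for the safety tables, so there is no figure to reproduce on this point. The only sample-size figure is power above 80% (Protocol Section 18.3, SAP Section 4.2). With CV 0.35, the log-scale SD is √ln(1 + 0.35²) = 0.340. The distance to the bound is ln(0.6/0.4) = 0.405, and the standard error is 0.340 × √(1/24 + 1/12) = 0.120. A normal approximation with a 90% interval gives 95.8%. The statement holds and uses no safety data.

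**Step 1: the rules side by side.**

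| Source | Who and what | Cut at withdrawal? |
|---|---|---|
| SAP 4.9, parenthesis | Subjects who discontinue from the study; all summaries and analyses | Yes |
| SAP 4.1 | Everyone given the planned single dose | No |
| SAP 4.4, AEs | Events after dosing, safety population | No |
| SAP 4.4, shift tables | "changes to the worst highest grade assessed post-dose during the study" | Unclear |
| Protocol 18.6 | All AEs, ECGs, laboratory data, examinations, vital signs | No |
| Protocol 8.1 | Safety follow-up after withdrawal, where possible | Such data may exist |

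The first row is inconsistent with the second, third and fifth. The last row is why this can matter in practice.

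**Step 2: effect on an incidence.** SAP Section 4.4 counts a subject once per category. If k subjects in a group of n each have their only event in a category after withdrawal, the tabulated incidence falls by 100 × k/n percentage points. Planned sizes are IV 12, active SC 4 + 20 = 24, placebo SC 2 + 4 = 6, and overall 42. For k = 1:

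- IV: 1/12 = 8.3 points
- Active SC: 1/24 = 4.2 points
- Placebo SC: 1/6 = 16.7 points
- Overall: 1/42 = 2.4 points

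The change is 0 if k = 0, or if the subject already had an event in that category before withdrawal.

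**Step 3: scheduled assessments at stake** (Protocol Tables 4 and 5), for a withdrawn subject who still attends.

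- Chemistry, hematology and coagulation are taken post-dose on Days 2, 5, 8, 15, 29, 43, 57, 90, 120, 150 and 200, which is 11 time points. Withdrawal just after Day 5 leaves 9 of 11 outside the summaries; just after Day 90, 3 of 11.
- ECGs are taken 15 minutes after the end of dosing and on Days 2, 3, 5, 150 and 200, which is 6 time points. Withdrawal after Day 5 and before Day 150 leaves 2 of 6 outside.
- ADA is sampled post-dose on Days 15, 29, 57, 90, 120, 150 and 200, which is 7 time points. Withdrawal just after Day 5 leaves all 7 outside; just after Day 90, 3 of 7. This assumes that ADA sampling is part of the continued safety follow-up; Protocol Section 15 lists it among the safety assessments.

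**The case against.** The best reply is that the parenthesis only glosses the sentence on imputation, and a gloss should not create a wider exclusion than the sentence it explains. Section 4.4 is the dedicated safety section, sets no cut, and can be read as governing. The moment of discontinuation is also undefined: if it means last contact, a subject who still attends has nothing beyond it.

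These readings are fair, and the first is probably what was meant. They make the clause ambiguous without settling it. Protocol Section 8.1 treats withdrawing and the end of follow-up as different things, and the SAP has no precedence rule. The pre-lock reassessment is optional and concerns missing values, not observed ones.

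Several stronger readings are tempting but not supported:

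- *The sponsor has chosen to discard safety data, or events would vanish from the report.* The wording points to a drafting slip, and the by-subject listings would still carry the events.
- *The late-reporting rules prove the conflict.* For SAEs the protocol says "There is no time limit for SAEs that are considered causally related", and it follows a pregnant subject to outcome "even if the subject discontinues study drug or discontinues from the study". These are reporting duties. Neither section says that such late reports enter the SAP tables, even for completers.
- *The shift-table rule plainly contradicts Section 4.9.* Its reference to the study period can be read as ending when the subject leaves.
- *The figures should be doubled because two discontinuations can trigger extra enrolment.* That trigger is tied neither to one treatment group nor to subjects with late events.
- *Subjects whose dosing is stopped for a severe reaction are lost.* Protocol Section 12.6 has them complete all scheduled visits, and the clause concerns leaving the study.

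**Conclusion.** The point holds as a wording defect that should be corrected. Followed as written, SAP Section 4.9 would leave observed safety and ADA results out of the summary tables after study discontinuation, against SAP Sections 4.1 and 4.4 and Protocol Section 18.6. The consequence is limited to tables that understate incidence or worst grade and disagree with the listings.

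The size is conditional. It requires a dosed subject who withdraws, is still observed, and has a first or worse finding only afterwards. The documents do not say how often that will happen, and it may not happen at all. The one-subject changes in the working are ceilings at the planned group sizes. The table shells to which SAP Section 5 refers were not available and might already resolve the matter.

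**What to change.** Keep the sentence on no further imputation and the existing date and concentration rules. Replace only the parenthesis with:

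*(no values will be imputed after a subject discontinues from the study; all safety data, including ADA results, observed after dosing and through the subject's last study assessment, including assessments made after withdrawal, will be included in the summaries under Sections 4.4 and 4.8)*

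Naming Section 4.8 is necessary because ADA is a safety endpoint analysed outside Section 4.4, and the last study assessment gives the window an end. PK handling stays with Section 4.5, and PD with the existing sentence in Section 4.9.

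The cost is one parenthesis in the SAP and a check that the table programs follow it. No new data are needed, since these results are already planned for collection and listing, and no clinical procedure changes.
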